The Summaries of Product Characteristics (SmPCs) for flupirtine-containing medicinal products have been revised accordingly by Lupin in February 2014 and MAHs marketing flupirtine-containing medicinal products in Germany in September/October 2013.

Additionally the PRAC requested that the MAHs should submit a risk management plan (RMP). The protocols of two studies - a drug utilisation study (DUS) and a PASS - should be submitted as part of the RMP.

This protocol covers a design for a DUS based on the information captured in longitudinal patient-level databases and has been set up accordingly to fulfill the conditions of the authority.

Research question and objectives

The aims of this study are to characterise prescribing practices for flupirtine-medicinal products during routine clinical use and to evaluate co-prescriptions and therapies of patients treated with Flupirtine products before and after the revision of the SmPC.

The analysis will display:

- Number of Flupirtine patients per specialty, per region (East/West Germany) and overall patients in the office
- Patient demography (age, gender and insurance status)
- Diagnoses, related to Flupirtine prescriptions
 - Diagnoses explicitly associated with Flupirtine prescriptions
 - Co-diagnoses associated with Flupirtine prescriptions
- Therapies, related to Flupirtine patients
 - Co-prescriptions received by Flupirtine patients
 - Further therapies received by Flupirtine patients
- Flupirtine exposure
 - Dosage and therapy duration
 - Prescription length
 - Number of Flupirtine prescriptions
 - Single and repeat prescriptions
 - relevant treatment patterns if available
- Contraindications for use of NSAIDs or weak opioids
- Long-term medications (>14 days) leading to contraindications for the use of Flupirtine
- Liverfunctions test, if available within 1 week after exposure to Flupirtine

Study design

This study is implemented using a longitudinal patient level Electronic Medical Records (EMR) database for Germany, IMS[®] Disease Analyzer.

The DUS will be carried out in Germany as more than 90% of total prescriptions for flupirtine-containing medicinal products of MAHs in European Union Member States were issued in Germany.

Population

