Additionally the PRAC requested that the MAHs should submit a risk management plan (RMP) within 3 months after the EC decision. The protocols of two studies - a drug utilization study (DUS) and a PASS should be submitted as part of the RMP.

Hormosan Pharma GmbH launched Flupirtinmaleat-Hormosan 100 mg Hartkapseln in Germany on 31 July 2012, but the marketing of the product was stopped in January 2013. This decision was taken because of commercial and not for safety reasons. Any other MAs held by Lupin Group of companies within EU have not been launched yet. Therefore an extension of deadline for submitting the RMP (including the outline of DUS, PASS and educational material) was received by the Reference Member State (RMS) authority BfArM on 29 November 2013 as the products are currently not marketed.

This protocol covers a design for a DUS based on the information captured in longitudinal patient-level databases and has been designed to fulfill the conditions of the authority.

8. Research question and objectives

The Flupirtine DUS aims to characterise prescribing practices of flupirtine-medicinal products during routine clinical use and to assess the main reasons for prescription by representative groups of prescribers.

The analysis will display by specialty and by prevalent/incident status:

- Number of prescribing physicians
- Region of office (East/West Germany)
- Number of overall patients in the office
- Number of patients with at least one flupirtine containing product

- Patient characteristics: age, gender, insurance status, indication for Flupirtine prescription
- Flupirtine exposure:
 - Number of Flupirtine prescriptions per patient during the 12-month observation period
 - Recommended daily Flupirtine dose (by physicians)
 - Recommended Flupirtine treatment duration (by physicians)
 - Prescription length
 - Indications related to the Flupirtine prescription
 - Co diagnosis within analysis period
 - Concomitant prescription of drugs grouped by relevant ATC classes (Annex 3- ii)
- Administered long-term medications (>14 days) leading to contraindication use of Flupirtine
- Contraindications for use of NSAIDs or weak opioids
- Treatment patterns if available
- Liverfunctions test performed within 1 week after Flupirtine exposure start

9. Research methods

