9.7 Data analysis

9.7.1 General remarks

Data from specialist panels will not be combined. The data will be analysed separately by panel (PCP and orthopaedist panel) and for the period before and after SmPC review.

All analyses will be stratified by incident and prevalent users.

Study tables will reference the data source used for each set of results. The data will be presented graphically where useful.

The statistical unit will be the patient (for information such as demographical and clinical characteristics, medical history, contraindications) and the Flupirtine prescription (for information such as indication, number of prescriptions, recommended treatment duration, concomitant drug prescriptions).

The statistical analysis will be done descriptively. Missing values will be reported as missing and no imputation will be conducted. Descriptive tables will be compiled for all variables. Continuous variables will be presented with counts, means, medians, standard deviations, and minimum and maximum values. Categorical variables will be presented in frequency tables. Rates and 95% confidence intervals will be provided when relevant.

Data will be analysed using the statistical software SAS (SAS Institute Inc., Cary, USA) with version 9.3 or above.

All results will be presented in tables. In addition, parameters addressing the primary objectives and eligible for a comparison of time periods (assessment period and reference period) with respect to the effect of risk minimisation measures (for example flupirtine treatment duration) will be presented graphically e.g. by displaying plots or bar charts.

The following section will describe the analyses and definitions used for the DA (**IMS[®] Disease Analyzer**) database.

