A therapy duration exceeding 14 days will be considered as long-term treatment within a year time span. A long-term treatment known to lead to contraindications for the use of Flupirtine will be analyzed

Analyses:

- Number and percentage of long-term therapies leading to contraindication of Flupirtine

Concomitant diseases of Flupirtine patients

Diseases are assumed to be concomitant, if prescription issued prior or after 2 weeks to Flupirtine treatment within study period.

Analyses:

- Number and percentage of patients with concomitant diseases during observation period, grouped by ICD codes

Therapies related to Flupirtine treatment

Patients treated with Flupirtine will be monitored by analyzing all co-prescriptions within the observation window of 12 months prior to Flupirtine treatment start, grouped by diagnosis according to ICD-10 codes [selection of codes see Annex 3 (ii)].

Analyses:

Number and percentage of patients receiving co-medication during 12 months prior to Flupirtine treatment start grouped by diagnosis according to ICD-10 codes [selection of codes see Annex 3 (ii)].

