Annex 3. Additional information

i. List of flupirtine-containing medicinal products in Germany in 2014

Dolokadin 400mg Tabletten Retard
Flupirtinmaleat Winthrop® 400 mg Retardtabletten
Flupirtinmaleat Winthrop® 100 mg Hartkapseln
Flupigil® 100 mg Hartkapseln
Katadolon® S long
Katadolon®
Katadolon® Zäpfchen
Katadolon® Kinderzäpfchen
Katadolon® inject
Trancolong®
Trancopal® dolo
Trancopal® dolo Suppositorien

ii. Diseases associated with acute pain, acute pain episodes, acute pain exacerbations (selection)

G20-G26 Extrapyrarnidal and movement disorders

- G20 Parkinson disease
- G21 Secondary Parkinsonism
- G22 Parkinsonism in diseases classified elsewhere
- G23 Other degenerative diseases of basal ganglia

G35-G37 Demyelinating diseases of the central nervous system

- G35 Multiple sclerosis

G40-G47 Episodic and paroxysmal disorders

- G44 Other headache syndromes

M15-M19 Arthrosis

- M15 Polyarthrosis
- M16 Coxarthrosis [arthrosis of hip]
- M17 Gonarthrosis [arthrosis of knee]
- M18 Arthrosis of first carpometacarpal joint
- M19 Other arthrosis

M40-M43 Deforming dorsopathies

- M40 Kyphosis and lordosis
- M41 Scoliosis
- M42 Spinal osteochondrosis
- M43 Other deforming dorsopathies

M45-M49 Spondylopathies

- M45 Ankylosing spondylitis
- M46 Other inflammatory spondylopathies
- M47 Spondylosis
- M48 Otherspondylopathies
- M49 Spondylopathies in diseases classified elsewhere

M50-M54 Other dorsopathies

- M50 Cervical disc disorders
- M51 Other intervertebral disc disorders
- M53 Otherdorsopathies, not elsewhere classified
- M54 Dorsalgia

M60-M63 Disorders of muscles

- M60 Myositis
- M61 Calcification and ossification of muscle
- M62 Other disorders of muscle
- M63 Disorders of muscle in diseases classified elsewhere

M95-M99 Other disorders of the musculoskeletal system and connective tissue
M95 Other acquired deformities of musculoskeletal system and connective tissue
M96 Postprocedural musculoskeletal disorders, not elsewhere classified
M99 Biomechanical lesions, not elsewhere classified

R50-R69 General symptoms and signs
R51 Headache
R52 Pain, not elsewhere classified

Source:

- ICD-10-GM Version 2014, Internationale statistische Klassifikation der Krankheiten und verwandter Gesundheitsprobleme 10. Revision, German Modification Version 2014, <http://www.dimdi.de/static/de/klassi/icd-10-gm/kodesuche/onlinefassungen/htmlgm2014/>. Access 20.08.2014
- Source: <http://apps.who.int/classifications/icd10/browse/2010/en>

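### The co-prescription analysis in 9.7.2.1 covers the year before flupirtine start, per patient and by pain-related ICD-10 codes, which contradicts the protocol's own item of concomitant prescriptions by ATC class per flupirtine prescription

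*Protocol*

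**What the plan says.** The aim in the abstract is to "evaluate co-prescriptions and therapies of patients treated with Flupirtine products before and after the revision of the SmPC". Section 8 lists, under flupirtine exposure, "Concomitant prescription of drugs grouped by relevant ATC classes (Annex 3- ii"), and section 9.3 repeats the item among the variables: "Concomitant prescription of drugs grouped by relevant ATC classes". Section 9.7.1 assigns some items to the patient and others to "the Flupirtine prescription (for information such as indication, number of prescriptions, recommended treatment duration, concomitant drug prescriptions").

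The analysis itself is in 9.7.2.1 under Therapies related to Flupirtine treatment. The method is "analyzing all co-prescriptions within the observation window of 12 months prior to Flupirtine treatment start, grouped by diagnosis according to ICD-10 codes", with a pointer to Annex 3 (ii). The output is "Number and percentage of patients receiving co-medication during 12 months prior to Flupirtine treatment start grouped by diagnosis according to ICD-10 codes", with the same pointer. Annex 3-ii is headed "Diseases associated with acute pain, acute pain episodes, acute pain exacerbations (selection").

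The same section also plans a count and percentage of long-term therapies that lead to a contraindication for flupirtine. Its definition is "A therapy duration exceeding 14 days will be considered as long-term treatment within a year time span". The comparison of the two periods in 9.7.2.4 lists six parameters, none of them on co-medication.

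**The concern.** The protocol is not silent here. It fixes a window, a unit and a grouping for co-prescriptions, and each differs from what its objectives, variable list and general remarks call for. A programmer who follows 9.7.2.1 produces a table of medication before flupirtine and labels it co-medication. One who follows sections 8, 9.3 and 9.7.1 departs from the analysis section.

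Concurrent use is central to this study. One of the risk minimisation measures in section 7 concerns patients who take other drugs known to cause liver injury at the same time as flupirtine. Section 7 also reports potentially hepatotoxic co-medication in 25 of 49 liver failure cases (25/49 = 51%). A table of earlier medication does not answer how often such drugs are given together with flupirtine.

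**Working it through.** No figure in the plan has to be reproduced. The check sets the two specifications side by side.

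| Feature | Sections 8, 9.3 and 9.7.1 | Section 9.7.2.1 |
|---|---|---|
| Timing | Concomitant, listed under flupirtine exposure | 12 months before flupirtine start |
| Unit | Flupirtine prescription | Patient |
| Classification | ATC class | ICD-10 diagnosis |
| Code list | Annex 3-ii, cited in section 8 for ATC classes | Annex 3-ii, cited for ICD-10 codes |

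**Timing.** The window closes at flupirtine start. A drug first prescribed on that day or later is outside it. A drug that ended months earlier is inside it. For incident users this is sharper: section 9.2 defines them as having no flupirtine prescription in the 12 months before their first one in the observation year. Their window therefore contains no recorded flupirtine prescription, and a counted drug can be concurrent only if its supply runs on past the start, which the analysis does not examine. For prevalent users the window contains earlier flupirtine by definition, so some counted drugs may be concurrent with it, but nothing ties them to a flupirtine prescription.

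**Code list.** The three-character codes in Annex 3-ii, by block: G20–G23 (4), G35 (1), G44 (1), M15–M19 (5), M40–M43 (4), M45–M49 (5), M50, M51, M53 and M54 (4), M60–M63 (4), M95, M96 and M99 (3), R51 and R52 (2). The sum is 4+1+1+5+4+5+4+4+3+2 = 33. All are neurological, musculoskeletal or pain codes, and none is an ATC class. Section 9.3 marks the ATC item with note ii and the indication with note iii, while Annex 3 has only parts i and ii and the diagnoses are part ii. This suggests that an ATC list was dropped and the references shifted, but that is an inference.

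**Other places that could supply the analysis.**
- The long-term therapy analysis in 9.7.2.1 leaves out courses of 14 days or less, does not tie its year to a flupirtine prescription, and covers only contraindicating drugs.
- The exposure analyses in 9.7.2.2 contain no co-medication item.
- The paragraph on concomitant diseases in 9.7.2.1 uses a two-week window around flupirtine treatment, but its output is diseases by ICD code, not drugs.
- Section 9.7.1 promises a descriptive table for every variable, which nominally includes concomitant prescriptions by ATC class, but gives that table no window and no code list.

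**The case against.** The strongest reply is that the protocol covers more than the one paragraph suggests. Several stronger conclusions that a reader might draw do not hold.

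- *That drugs given with flupirtine would never be tabulated.* Section 9.7.1 promises tables for all variables, and section 9.3 lists the ATC item as a variable. Section 9.8 refers to a statistical analysis plan and table shells, which are not at hand. A missing window or ATC list could properly be settled there, so the absence of such detail is not the point.
- *That no other co-medication analysis exists.* The long-term contraindicating-therapy analysis is one, and its year is not restricted to the time before flupirtine start.
- *That a change between 2012 and 2014 could not be seen.* Section 9.7.1 has the data analysed separately for each period, so tables would stand side by side. The study is descriptive, without tests, and an informal comparison remains possible.
- *That drugs for conditions outside Annex 3-ii have no row.* The method speaks of all co-prescriptions. The output could mean patients grouped by pain diagnosis with all their drugs counted. The sentence is ambiguous.
- *That the share of counted drugs not overlapping flupirtine can be calculated.* The protocol gives no course lengths or timing for other drugs. Any such share would rest on an assumed pattern of use, and continuous long-term drugs would overlap far more than single short courses.

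It is also fair that overlap of supply is only one valid definition of concomitant use. All of this limits the point. None of it removes the conflict in timing, unit and classification, because 9.7.2.1 states a rule that an analysis plan would have to either follow or contradict.

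**Conclusion.** The point holds as an internal contradiction. The only section that specifies a general co-prescription analysis conflicts with the protocol's own objective, variable list and statistical unit on three features, and the annex cited for ATC classes contains none. Followed literally, it reports prior medication as co-medication and leaves out drugs first prescribed on or after flupirtine start. The omission from 9.7.2.4 is secondary: it leaves an aim of the abstract out of the formal comparison list, but does not prevent comparison across the period-specific tables.

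The effect on the reported percentages cannot be given from the documents. The conclusion rests only on reading the 12-month window as ending at flupirtine start, which is what the text says. This should be corrected before the analysis is programmed; in a descriptive study with a separate analysis of contraindicating drugs, its weight is moderate.

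**What to change.** Reconcile sections 8, 9.3, 9.7.1, 9.7.2.1 and 9.7.2.4 and the annex:

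1. In 9.7.2.1, tabulate concomitant prescriptions by ATC class with the flupirtine prescription as unit, in a stated window around the flupirtine prescription. Same day or a fixed number of days either side would serve; overlap of supply is an option where days of supply can be derived.
2. Keep the existing 12-month table, relabel it prior medication, and state whether the Annex 3-ii codes group the drugs or the patients.
3. Correct the annex reference in section 8 and add the list of ATC classes.
4. Add the ATC-class percentages to the comparison in 9.7.2.4.

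No new data are needed: Table 1 in section 9.4 lists visit date, product and quantity, ATC and co-prescription. The cost is wording plus a further set of tables across 2 panels × 2 periods × 2 user groups = 8 strata. If overlap of supply is chosen, defined daily doses would have to be assumed for co-prescribed drugs without usable dosage advice; a same-day or fixed window avoids this.

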9.7.2.2 Flupirtine exposure

Flupirtine exposure will be defined as one or more prescriptions of Flupirtine. These prescriptions will be identified using the ATC code for Flupirtine or INN. The Flupirtine exposure start date (i.e. the cohort entry date) for each patient will be defined as the date of the first record of Flupirtine prescription during each of the defined twelve-month patient selection window.

Treatment duration

The treatment duration (in days) will be evaluated by using the recommended treatment duration by the physician. If this is not available, the treatment duration cannot be determined exactly as the dose recommendation “as required (pro re nata)” is very often given in the therapy of acute pain. Therefore, the percentage of patients with no information according to recommendation by the physician will be determined.

Prescription length

The prescription length (in days) will be determined as follows:

- For prescriptions with available information on recommended dose per day: from the prescription date plus the expected number of days of drug supply based on the package size and the recommended daily dose
- For all prescriptions without recommendation of dosage: from the prescription date plus the expected number of days of drug supply based on the package size and the DDD(400 mg / day)

The prescription length is therefore not necessarily identical to the treatment duration.

The following parameters will be considered in the analysis for each Flupirtine prescription:

- Date of prescription
- Recommended daily dose by physician
- Recommended treatment duration by physician

Analyses:

- Number and percentage of patients with prescriptions of a flupirtine-containing medicinal product during the 12-month patient selection window
- Treatment duration in days
- Prescription length
- Single use and repeated use

Treatment episodes

A treatment episode will be defined as one or more prescriptions (repeated prescriptions) of flupirtine with gaps between prescription length not more than 7 days. In the case the gap between the prescriptions is longer than 7 days it will be considered as two subsequent treatment episodes. The analysis of treatment episodes will consider prescription length based on DDD, because for all prescriptions this information will be available.

Analyses:

- Number and percentage of episodes
- Min, max, mean, median length of episodes
- Patients within each episode

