Drug utilisation study (DUS) on flupirtine-containing medicinal products.

Retrospective drug utilisation study using patient-level databases to characterise prescribing practices of flupirtine-containing medicinal products during routine clinical use and assess the main reasons for prescription by representative groups of prescribers.

Rationale and background

Due to a rising number of hepatotoxicity reactions during treatment with flupirtine containing products the Co-ordination Group for Mutual Recognition and Decentralised Procedures – Human (CMDh) recommended on 28 June 2013 to restrict the use of oral Flupirtine medicines and suppositories as following:

- treatment of acute (short-term) pain in adults who cannot use other painkillers, such as non-steroidal anti-inflammatory drug (NSAIDs) and weak opioids
- treatment duration limited to not longer than 2 weeks
- after each full week of treatment patients' liver function should be checked
- treatment termination if any signs of liver problems occur
- contraindicated for patients with preexisting liver disease or alcohol abuse problems
- contraindicated for patients taking other medications known to cause liver problems

The recommendations follow a review by the EMA's Pharmacovigilance Risk Assessment Committee (PRAC) which looked into reported liver problems with Flupirtine, ranging from high liver-enzyme levels to liver failure. The PRAC evaluated the available data on liver safety, noting that there were no cases of liver failure or liver transplantation reported in patients who took the medicine for 2 weeks or less. The PRAC also reviewed the available data on the benefits of Flupirtine and concluded that, while there were data from studies in the treatment of acute pain, there were insufficient data to support its use in the treatment of long-term pain.

The CMDh agreed with the PRAC's conclusions and endorsed the PRAC's recommendations on the use of flupirtine-containing medicines. The CMDh position was sent to the European Commission (EC), which endorsed it and adopted a final legally binding decision valid throughout the EU on 5 September 2013.

The reported outcomes were communicated to healthcare professionals by all Germany marketing authorisation holders (MAHs) via a joint Direct Healthcare Professional Communication (DHPC) distributed in July 2013.

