The PRAC initiated a subsequent benefit-risk evaluation and considered that the controlled clinical studies required by the Note for guidance on clinical investigation of medicinal products for treatment of nociceptive pain (CPMP/EWP/612/00, issued 21 November 2002) for long-term treatment of chronic pain are not available for flupirtine-containing medicinal products². Based on the fact of observed liver effects recorded during long-treatment with Flupirtine and on the absence of controlled long-term clinical studies, the PRAC noted that the management of chronic pain is no longer favourable in terms of the benefit-risk balance for flupirtine-containing medicinal products. The PRAC adopted a recommendation on 13 June 2013 under the provisions of article 107i of Directive 2001/83/EC³.

Taking the currently available data into account, the PRAC decided that the benefit-risk balance for flupirtine-containing products is favourable in the treatment of acute pain, subject to implementation of the following risk minimisation measures⁴:

- Limitation of indication to acute pain in adults if treatment with other analgesics (e.g. NSAIDs, weak opioids) is contraindicated.
- Restriction of Flupirtine use to a maximum of two weeks of treatment.
- Contraindication of Flupirtine in patients with pre-existing liver disease or alcohol abuse.
- Contraindication of Flupirtine in patients concomitantly taking other medications which are known to cause Drug Induced Liver Injury (DILI).

- Weekly liver function tests during treatment and discontinuation in the case of abnormal liver function tests or clinical symptoms.

The PRAC imposed a DHPC, which was distributed on 15 July 2013, in order to communicate the outcome of the PRAC/EMA decision to healthcare professionals⁵. The SmPCs for flupirtine-containing medicinal products have been revised accordingly by Lupin in February 2014 and MAHS marketing flupirtine-containing medicinal products in September/October 2013⁶. The educational material was distributed in February 2015.

Patients and prescribers have been provided with joint educational material according to the PRAC request, prepared jointly by all German MAHs. The educational material, the DUS and a PASS protocol are parts of the RMP.

As of 5 September 2013, the European Commission implemented the decision (C(2013) 5788 final) with the majority opinion of the CMD(h) addressed to all member states based on the PRAC's recommendation⁷.

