9.2. Setting

The study will be conducted in the outpatient setting in Germany.

Study population

All patients with a record of Flupirtine prescription during the defined 12-month periods (patient selection window) will be identified from selected database.

The study will include both single users and recurrent users of flupirtine-containing medicinal products.

The study will include two cohorts of patients:

- patients initiated on flupirtine treatment after the review of SmPC in Germany
- patients treated with flupirtine before the review of SmPC in Germany

The two cohorts will include:

- Incident user: patients who had one or more flupirtine prescriptions during the one-year observational period, but no flupirtine prescription for at least 12 months prior to the first flupirtine prescription during the observational period
- Prevalent user: patients who had one or more flupirtine prescriptions during the one-year observational period and at least one flupirtine prescription during the 12 months prior to the first flupirtine prescription during the observational period

Inclusion criteria:

Eligible patients must have at least one prescription of Flupirtine (exposure) during the defined 12-month observational period.

Exclusion criteria:

Exclusion criteria will not be applied.

Study period

The selection of patients from the IMS[®] Disease Analyzer will be carried out in two defined 12-month periods from January 1, 2012 to December 31, 2012 and January 1, 2014 to December 31, 2014, respectively (patient selection window). The date of the first prescription fill in each period will be defined as the exposure start date.

Pre-exposure period:

In order to obtain information about medical history before Flupirtine exposure start, a time period of at least 12 months prior to the individual Flupirtine exposure start date will be analysed for each patient for whom these data are available.

Follow-up:

A follow-up period of one to six months after the exposure start date will be monitored for all patients, and till the end of analysis period for whom these data are available.

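### Exposure covers every flupirtine form, including a listed injection, while the protocol words the scope of the restrictions in two ways and the pre-post comparison does not separate forms

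*Protocol*

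**What the plan says.** **Exposure.** Section 9.7.2.2 identifies flupirtine prescriptions by substance only: "These prescriptions will be identified using the ATC code for Flupirtine or INN". Section 9.2 sets the entry rule, "Eligible patients must have at least one prescription of Flupirtine (exposure) during the defined 12-month observational period", and adds "Exclusion criteria will not be applied". Nothing later removes a pharmaceutical form.

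**Products.** Annex 3(i), the list of flupirtine products in Germany in 2014, includes "Katadolon® inject" and a children's suppository beside the oral products and other suppositories.

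**Scope of the restrictions.** The Abstract (Rationale and background) describes the CMDh recommendation as one "to restrict the use of oral Flupirtine medicines and suppositories as following". Section 7 sets no limit by form. It describes the BfArM intention as covering all flupirtine-containing medications, and introduces the PRAC measures with the statement that "the benefit-risk balance for flupirtine-containing products is favourable in the treatment of acute pain", subject to those measures. The SmPC revision is likewise described for flupirtine-containing products.

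**Comparison.** Section 9.7.1 ties the comparison of periods to the effect of the risk minimisation measures. Section 9.7.2.4 lists six parameters, analysed by physician panel and by incident or prevalent status. Form is not a stratum.

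**Supply length.** In 9.7.2.2, prescription length uses the physician's daily dose where recorded and a DDD of 400 mg/day otherwise. The treatment-episode analysis uses the DDD-based length for all prescriptions.

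**The concern.** The comparison is meant to show what changed after the measures. On the Abstract's wording, an injection is not addressed by them, yet any injection record would enter the percentages in 9.7.2.4.

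This could matter in two ways. If the covered forms change and the injection does not, the pooled change is diluted. If prescribing of the covered forms falls while injection use stays level, the injection makes up a larger part of the 2014 users. Pooled percentages can then move although prescribing within each form has not changed, and a larger sample does not remove such a shift.

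A related issue does not depend on which scope wording is right. In the episode analysis one daily figure converts packs of injections, children's suppositories and adult oral products into days. Two of the six parameters rest on that conversion: episode length, and patients with an episode longer than 14 days.

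**Working it through.** **1. The plan's own figures.** Section 9.5, Table 2 gives patients with 12 months' history and applies a 25% reduction.

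- PCP: 11,284 × 0.75 = 8,463 (stated 8,463).
- Orthopaedist: 1,821 × 0.75 = 1,365.75 (stated 1,365).

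Both reproduce. They are used here only to judge scale.

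**2. Assumptions.** The documents give no injection share and no form-specific percentages. Assumed:

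- injection share of 2012 users, s = 1%, 2% or 5%;
- injection use constant;
- users of the other forms falling by d = 25% or 50%;
- single use 50% among other users and 100% among injection users, in both periods.

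The 25% matches the hypothetical decrease in Section 9.5. Section 9.4 gives about 39,000 PCP and 15,000 orthopaedist patients over 24 months, so the mean annual counts were at least about 19,500 and 7,500. Table 2 shows 14,743 and 4,635 for July 2013 to June 2014. If the panels were stable, the falls were at least 1 − 14,743/19,500 = 24% and 1 − 4,635/7,500 = 38%. These counts cover all forms together.

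**3. Injection share in 2014.** s14 = s / [s + (1 − s)(1 − d)]. The single-use shift is (s14 − s) × (100 − 50) points.

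| s | d | s14 | Shift (points) |
|---|---|---|---|
| 1% | 25% | 0.01/0.7525 = 1.33% | 0.16 |
| 1% | 50% | 0.01/0.505 = 1.98% | 0.49 |
| 2% | 25% | 0.02/0.755 = 2.65% | 0.32 |
| 2% | 50% | 0.02/0.51 = 3.92% | 0.96 |
| 5% | 25% | 0.05/0.7625 = 6.56% | 0.78 |
| 5% | 50% | 0.05/0.525 = 9.52% | 2.26 |

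**4. Scale.** The largest 95% half-width for one percentage (p = 0.5) is 1.96 × √(0.25/n): 1.07 points at n = 8,463 and 2.65 points at n = 1,365. For a difference between two periods of equal size, multiply by √2: 1.51 and 3.75 points. Incident and prevalent strata are smaller, so their intervals are wider. Only the 5%/50% case (2.26) exceeds the PCP half-widths; none exceeds the orthopaedist ones.

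**5. Distortion within one period.** Pooling shifts a percentage by f × gap, where f is the injection share. With a 50-point gap this is 0.5 points at f = 1% and 2.5 at f = 5%. It passes the single-percentage half-width only above f = 1.07/50 = 2.1% (PCP) or 2.65/50 = 5.3% (orthopaedist).

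**6. Dilution.** Suppose the covered forms change by 20 points, the injection does not change, and its share is the same in both periods. The pooled change is 20 × (1 − f): 19.8 points at 1%, 19.0 at 5%.

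**The case against.** A reader might infer that the planned percentages do mix restricted and unrestricted use. The documents do not support that. Nowhere do they call the injection unrestricted. Section 7 words the BfArM intention, the PRAC measures and the SmPC revision without a limit by form, and the Abstract itself says the CMDh endorsed the PRAC recommendations on flupirtine-containing medicines. If that wording governs, the injection is inside the measures and there is nothing to separate on grounds of scope.

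Nor do the documents show injection records in the data. Annex 3(i) is a product list, not a count of prescriptions, and the setting is PCP and orthopaedist practices. Every share above is assumed, and the results at 1% to 2% lie below the largest full-panel half-widths. Nothing in the protocol fixes the direction for liver function monitoring or episode length either.

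Capturing the whole substance also suits a descriptive utilisation study, and a breakdown by form could sit in the table shells, which are not at hand. All of this stands.

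Three things remain. The two statements of scope differ. The protocol fixes a comparison aimed at the measures without saying which forms count. The single DDD conversion in the episode analysis applies whichever scope is right.

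Limiting the episode analysis to adults may also look like a remedy for that conversion. It would remove from view use in patients under 18, which a utilisation study should show and which 9.7.2.1 already plans to count.

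**Conclusion.** The point holds conditionally and is minor. The protocol defines exposure for all forms, lists an injectable product, and describes the restrictions once for oral medicines and suppositories and elsewhere for flupirtine-containing products generally. If the narrower scope is correct and injections occur in the panels, the 9.7.2.4 percentages include use outside the measures and can shift by composition.

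Under the stated assumptions the single-use percentage would shift by about 0.2 to 2.3 points. That range rests entirely on assumed shares, constant injection use and an assumed 50-point gap; with few or no injection records the effect is negligible. No such range is offered for the other parameters, because the documents give nothing to anchor it.

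**What to change.** 1. Reconcile the Abstract with Section 7 on which pharmaceutical forms the measures cover, and state the answer once in 9.7.2.2.
2. In 9.7.2.4, report the number of injectable prescriptions and patients per period and panel. Base the pre-post comparison on the covered forms, or show it with and without the injection.
3. In the DDD-based episode analysis, show injections, children's suppositories and patients under 18 as separate rows. Keep patients under 18 in the study's description of use.

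The data are held already: Table 1 in Section 9.4 lists product and age among the database variables. The cost is a few extra table rows, a line or two of protocol text and a slightly smaller denominator for the comparison. If the injection count is close to zero, the row that reports it settles the question.
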